4.1.2 Exclusion Criteria

Patients who meet any of the following criteria will be excluded from study entry:

- Any prior treatment for primary invasive breast cancer
- Patients with cT4 or cN3 stage breast tumors
- Metastatic (Stage IV) breast cancer
- Bilateral invasive breast cancer
- Multicentric breast cancer (the presence of more than one tumor in different quadrants of the breast)
- Patients who have undergone excisional biopsy of primary tumor and/or axillary lymph nodes
- Patients who have undergone sentinel lymph node biopsy prior to study treatment
- Patients for whom upfront chemotherapy is clinically judged appropriate as optimal neoadjuvant treatment
- Patients for whom immediate surgery is indicated
- Type 1 or 2 diabetes requiring antihyperglycemic medication
- Inability or unwillingness to swallow pills
- Malabsorption syndrome or other condition that would interfere with enteric absorption
- History of prior or currently active small or large intestine inflammation (such as Crohn's disease or ulcerative colitis). *Any patient with a baseline medical condition involving the gastrointestinal (GI) tract or who may have a predisposition for GI toxicity requires prior approval from the Medical Monitor.*
- Congenital long QT syndrome or QT interval corrected using Fridericia's formula (QTcF) > 470 msec
- $\text{DL}_{\text{CO}} < 60\%$ of the predicted values (see [Appendix 7](#) for calculations)

- Clinically significant (i.e., active) cardiovascular disease, uncontrolled hypertension, unstable angina, history of myocardial infarction, cardiac failure class II–IV (New York Heart Association, [Appendix 5](#)), or any other that in the judgment of the investigator could jeopardize patient safety or study outcomes
- Any contraindication to MRI examination, including the following:
 - Neurostimulators
 - Pacemakers
 - Implanted metallic material or devices (metal implants or large tattoos in the field of view)
 - Severe claustrophobia
 - Physical characteristics (weight and/or size) that exceed the capabilities of the MRI scanner
 - Known allergy or hypersensitivity reactions to gadolinium, versetamide, or any of the inert ingredients in gadolinium-based contrast agents
 - Severe renal insufficiency, e.g., estimated glomerular filtration rate < 30 mL/min
- Active infection requiring intravenous (IV) antibiotics
- Patients requiring any daily supplemental oxygen
- Clinically significant history of liver disease, including viral or other known hepatitis, current alcohol abuse, or cirrhosis
- Known HIV infection
- Any other diseases, active or uncontrolled pulmonary dysfunction, metabolic dysfunction, physical examination finding, or clinical laboratory finding giving reasonable suspicion of a disease or condition that contraindicates the use of an investigational drug, that may affect the interpretation of the results, or renders the patients at high risk from treatment complications
- Significant traumatic injury within 3 weeks prior to initiation of study treatment
- Major surgical procedure within 4 weeks prior to initiation of study treatment
- Inability to comply with study and follow-up procedures
- History of other malignancy within 5 years prior to screening, except for appropriately treated carcinoma in situ of the cervix, non-melanoma skin carcinoma, or Stage I uterine cancer

4.2 METHOD OF TREATMENT ASSIGNMENT AND BLINDING

4.2.1 Patient Randomization

After written informed consent has been obtained and eligibility has been established, the study site will obtain a patient's identification number and treatment assignment using a permuted block randomization algorithm via an interactive voice or Web-based response system (IxRS).

4.2.2 Stratification

Patients will be randomized into one of the two treatment arms in a 1:1 ratio based on the following stratification factors:

- Tumor size (T1–2 vs. T3)
- Nodal status (cytologically positive vs. radiologically or cytologically negative). If on ultrasound examination there is evidence of suspicious axillary lymph nodes at the baseline examination, then fine needle aspiration (FNA) or core biopsy is required to confirm nodal status.

4.2.3 Blinding

Investigators and patients will be blinded to treatment assignment of GDC-0032 or placebo.

For emergency situations, the investigator will be able to break the treatment code by contacting the IxRS. The responsibility to break the treatment code in emergency situations resides solely with the investigator. For non-emergency situations, the investigator needs to obtain approval from the Medical Monitor to break the treatment code. Unblinding during the study will result in the withdrawal of a patient from the study. For regulatory reporting purposes, and if required by local health authorities, the Sponsor will break the treatment code for all serious, unexpected, suspected adverse reactions that are considered by the investigator or Sponsor to be related to study drug.

While PK samples must be collected from patients assigned to the comparator arm to maintain the blinding of treatment assignment, PK assay results for these patients are generally not needed for the safe conduct or proper interpretation of this trial. The PK assay group will be unblinded to patients' treatment assignments to identify appropriate PK samples to be analyzed and bioanalytical methodology to employ. However, the PK scientist does not have access to the PK assay results and therefore stays blinded until the PK assay results need to be interpreted and reported. Samples from patients assigned to the comparator arm will be analyzed for letrozole. However, GDC-0032 assay will be analyzed by request (i.e., to evaluate a possible error in dosing).

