4.6 PATIENT, TREATMENT, STUDY, AND SITE DISCONTINUATION

4.6.1 Patient Discontinuation

Patients have the right to voluntarily withdraw from the study at any time for any reason. In addition, the investigator has the right to withdraw a patient from the study at any time. Reasons for withdrawal from the study may include but are not limited to the following:

- Patient withdrawal of consent at any time
- Any medical condition that the investigator or Sponsor determines may jeopardize the patient's safety if he or she continues in the study
- Investigator or Sponsor determines it is in the best interest of the patient
- Patient non-compliance

Every effort should be made to obtain information on patients who withdraw from the study. The primary reason for withdrawal from the study should be documented on the appropriate eCRF. However, patients will not be followed for any reason after consent has been withdrawn. Patients who withdraw from the study will not be replaced.

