5.6 POST-STUDY ADVERSE EVENTS

At the time of study completion or study discontinuation, the investigator should instruct each patient to report to the investigator any subsequent adverse events that the patient's personal physician believes could be related to prior study drug treatment or study procedures.

The investigator is not required to actively monitor patients for adverse events after the end of the adverse event reporting period (30 days after the last dose of study drug). However, the Sponsor should be notified if the investigator becomes aware of any death, other serious adverse event, or adverse event of special interest occurring after the end of the adverse event reporting period, regardless of causality. The Sponsor should also be notified if the investigator becomes aware of the development of cancer or a congenital anomaly/birth defect in a subsequently conceived offspring of a female patient exposed to study drug or the female partner of a male patient exposed to study drug.

The investigator should report these events *directly to the Sponsor or its designee, either by faxing or by scanning and emailing the Serious Adverse Event/Adverse Event of Special Interest Reporting Form using the fax number or email address provided to investigators* (see "Protocol Administrative and Contact Information & List of Investigators").

5.7 EXPEDITED REPORTING TO HEALTH AUTHORITIES, INVESTIGATORS, INSTITUTIONAL REVIEW BOARDS, AND ETHICS COMMITTEES

The Sponsor will promptly evaluate all serious adverse events and adverse events of special interest against cumulative product experience to identify and expeditiously communicate possible new safety findings to investigators, IRBs, ECs, and applicable health authorities based on applicable legislation.

To determine reporting requirements for single adverse event cases, the Sponsor will assess the expectedness of these events using the following reference documents:

- GDC-0032 Investigator's Brochure
- Local prescribing information for letrozole SmPC

The Sponsor will compare the severity of each event and the cumulative event frequency reported for the study with the severity and frequency reported in the applicable reference document.

Reporting requirements will also be based on the investigator's assessment of causality and seriousness, with allowance for upgrading by the Sponsor as needed.

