6.1 DETERMINATION OF SAMPLE SIZE

This study is designed for testing the effect of GDC-0032 on the two co-primary endpoints in all enrolled patients and in the *PIK3CA* MT patients and plans to enroll 330 patients in total. Assuming the *PIK3CA* mutation status will not be available (unknown) for approximately 10% of the patients and the prevalence of *PIK3CA* mutant is 40%, there will be approximately 120 patients in the *PIK3CA* MT cohort.

Given that the *PIK3CA* mutation status is not a stratification factor for randomization, there might be a possible imbalance between treatment arms within the *PIK3CA* MT cohort, which may reduce the statistical power in this cohort. To ensure the study provides sufficient statistical power even when the treatment assignment is imbalanced, the sample size was calculated based on a conservative scenario by assuming that the treatment assignment imbalance in *PIK3CA* MT is 40% versus 60%. The sample size was calculated based on a chi²-test using continuity correction ([Ury and Fleiss 1980](#)).

To control an overall, two-sided, family-wise error rate under 20% *for each analysis population*, we use a two-sided significance level of 16% and 4% for the co-primary endpoints MRI ORR, and pCR, respectively.

Assuming 10% of the patients are unevaluable for the MRI ORR, approximately 300 enrolled patients and 108 patients in the *PIK3CA* MT cohort will be evaluable for analyses. This sample size allows us to detect an absolute percentage increase of 24% in MRI ORR rate in the GDC-0032 plus letrozole arm (64%) versus the letrozole-only

arm (40%; [Smith et al. 2005](#); [Ellis and Ma 2007](#)) in the *PIK3CA* MT cohort at 80% power and 16% two-sided significance level. The minimal detectable difference for ORR is approximately 15%.

Assuming that all patients are evaluable for pCR (i.e., approximately 330 enrolled patients and 120 in the *PIK3CA* MT cohort), this sample size provides 80% power to detect an absolute percentage increase of 18% in pCR in the GDC-0032 plus letrozole arm (19%) versus the letrozole-only arm (1%, [Smith et al. 2005](#); [Ellis and Ma 2007](#)) in the *PIK3CA* MT cohort at the 4% two-sided significance level. The minimal detectable difference for pCR rate is approximately 13%.

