6.4 EFFICACY ANALYSES

The primary and secondary efficacy analyses will include the ITT population; that is, all randomized patients will be included in the analyses, with patients grouped according to the treatment assigned at randomization.

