6.4.1 Primary Efficacy Endpoint

The co-primary efficacy endpoints are (1) tumor ORR, assessed by modified RECIST criteria by breast MRI (centrally assessed) and (2) the rate of pCR in breast and axilla (total pCR) after completion of study drug.

The tumor ORR will be calculated by treatment arm in all enrolled population and in *PIK3CA* MT population. Within each population, the ORR for the two treatment arms will be compared at a two-sided alpha of 16% using a Cochran Mantel-Haenszel test, stratified by tumor size and nodal status. The pCR rate will also be calculated and compared at a two-sided alpha of 4% based on the same analytical approach as ORR. The two alpha values account for a family-wise type I error rate of 20% *for each analysis*

population. Patients with early study termination and hence missing efficacy outcome will be considered as non-responders.

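### Section 4.2.3 ends study participation, not only blinded treatment, when a patient is unblinded, so a co-primary outcome can go uncollected and be scored as non-response

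*Protocol*

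**What the plan says.** Section 4.2.3 (Blinding) lets the investigator break the code in an emergency, and otherwise with the Medical Monitor's approval. It then says: "Unblinding during the study will result in the withdrawal of a patient from the study". The sentence is not limited by reason, by timing or by who breaks the code. The next sentence adds that, for regulatory reporting, "the Sponsor will break the treatment code for all serious, unexpected, suspected adverse reactions" considered related to study drug.

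The protocol treats leaving the study (Section 4.6.1) and stopping treatment (Section 4.6.2) as different things, and Section 4.2.3 uses the first. On withdrawn patients, Section 4.6.1 says: "Every effort should be made to obtain information on patients who withdraw from the study". It rules out follow-up only once consent has been withdrawn.

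For both co-primary endpoints, Section 6.4.1 says: "Patients with early study termination and hence missing efficacy outcome will be considered as non-responders".

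**The concern.** Breaking the code affects the blind. It does not prevent an MRI or a surgical specimen from being obtained. These patients have breast cancer eligible for primary surgery (Section 4.1.1), the MRI endpoint is centrally read, and pCR comes from local pathology (Section 4.5.9). A rule that ends study participation at unblinding therefore risks losing outcomes that could have been had, and Section 6.4.1 turns each lost outcome into a failure.

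The loss need not be balanced. Codes are usually broken because of a suspected drug reaction. Section 1.7.1 reports GDC-0032-related diarrhea in 67% of patients given the drug with letrozole, 11% at Grade 3 or 4. That makes an excess in the GDC-0032 arm plausible. It would pull both co-primary comparisons toward no effect and weaken post-surgical safety follow-up in the patients where it is most informative.

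**Working it through.** **Inputs (Section 6.1).** PIK3CA-mutant cohort, split 40:60, taken here as 40% control and 60% GDC-0032. ORR 40% versus 64%, 108 evaluable. pCR 1% versus 19%, 120 evaluable. Chi-square test with continuity correction, 80% power, and for alpha "we use a two-sided significance level of 16% and 4% for the co-primary endpoints MRI ORR, and pCR, respectively". The share w of the GDC-0032 arm lost through unblinding is not in the protocol and is assumed to be 1% to 5%.

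**Step 1: reproduce the plan.** With d = p2 − p1, r = 1.5, and p̄ the average of p1 and p2 weighted by allocation:

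- Uncorrected control n′ = [z(1−α/2)·√((r+1)·p̄(1−p̄)) + z(0.80)·√(r·p1(1−p1) + p2(1−p2))]² / (r·d²).
- Corrected control n = (n′/4)·[1 + √(1 + 2(r+1)/(n′·r·d))]².
- ORR: n′ = 36, corrected to 43; total 43 + 64.5 = 107.5, against 108 stated.
- pCR: n′ = 40, corrected to 49; total 49 + 73.5 = 122.5, against 120 stated.

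The design figures reproduce.

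**Step 2: power at the stated sizes.** Power = Φ{[d − ½(1/n1 + 1/n2) − z(1−α/2)·√(p̄(1−p̄)(1/n1 + 1/n2))] / √(p1(1−p1)/n1 + p2(1−p2)/n2)}.

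For ORR, n1 = 43.2, n2 = 64.8 and z = 1.405. The continuity term is 0.0193. With p̄ = 0.544, the null term is 1.405 × 0.0978 = 0.1375 and the denominator is 0.0955. Power = Φ[(0.24 − 0.0193 − 0.1375)/0.0955] = Φ(0.87) = 80.8%. The same formula gives 79.1% for pCR at 120.

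**Step 3: lose a share w of the GDC-0032 arm only, scored as non-response.** ORR becomes 0.64(1 − w) and pCR becomes 0.19(1 − w).

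| w | GDC-0032 ORR | ORR difference (points) | ORR power | pCR power |
|---|---|---|---|---|
| 0% | 64.0% | 24.0 | 80.8% | 79.1% |
| 1% | 63.4% | 23.4 | 78.9% | 78.3% |
| 2% | 62.7% | 22.7 | 76.9% | 77.6% |
| 3% | 62.1% | 22.1 | 74.7% | 76.8% |
| 5% | 60.8% | 20.8 | 70.2% | 75.2% |

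Each 1% lost costs 0.64 points of ORR difference and about 2 points of ORR power.

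**Step 4: other patterns.**

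- Equal loss in both arms: the difference is 24(1 − w). At 1% it is 23.8 points with power 80.1%; at 5% it is 22.8 points with power 77.1%.
- No true effect (40% in both arms), loss in the GDC-0032 arm only: bias is −0.40w, that is −0.4 points at 1% and −2.0 points at 5%.

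**Step 5: in patients.** With 330/2 = 165 in the GDC-0032 arm overall, 1% to 5% is about 2 to 8 patients. In the mutant cohort (0.6 × 108 ≈ 65) it is about 1 to 3.

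**The case against.** The case against is substantial, and four stronger readings should be resisted.

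1. *The sponsor's regulatory code break removes the patient.* A reader might infer this because nothing exempts it. But Section 4.2.3 opens by defining the blind as that of investigators and patients, and the withdrawal sentence follows the investigator rules and precedes the sponsor sentence. The same section leaves the PK assay group unblinded, and Section 3.1.2 has the iDMC review unblinded safety data. Neither can be meant to trigger withdrawal. The scope is unsettled, not established.

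2. *Withdrawal makes the outcome missing.* No section says so. Section 4.6.1 still asks for information, and Section 6.4.1 imputes only when the outcome is in fact missing. Unblinding after the Week 16 MRI (Days 106–112) and surgery loses neither endpoint, and Section 3.3.7 puts colitis onset at about 82 to 248 days. What remains is that Section 4.6.1 names neither the MRI nor the pathology, and Appendix 1 has no schedule for withdrawn patients.

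3. *The rule contradicts intention to treat.* It does not. Section 6.4 says "all randomized patients will be included in the analyses, with patients grouped according to the treatment assigned at randomization", and counting missing outcomes as failures keeps everyone in the analysis. The cost is avoidable imputation.

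4. *The GDC-0032 arm will be penalised by a known amount.* The direction is an inference. Sponsor code breaks cover only unexpected reactions, and under Section 5.7 "the Sponsor will assess the expectedness of these events using the following reference documents", so known toxicities may not qualify. Tables 2 to 7 manage the known toxicities as GDC-0032/placebo, largely without needing the code. Placebo patients can be unblinded too.

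The calculation is also unfavourable by construction. It assumes that every loss is early and complete, that these patients would have responded at the full 64%, and that the losses come on top of the 10% unevaluable allowance. Section 6.1 permits a larger sample if more patients are unevaluable. That could restore power but would not remove bias from unequal losses.

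**Conclusion.** The defect is real, and its effect cannot be sized from the protocol. Followed as written, Section 4.2.3 can create missing co-primary outcomes that need not be missing, Section 4.6.1 does not reliably prevent this, and Section 6.4.1 scores them as failures. The 1% to 5% results above are an assumed one-arm range, not a forecast, and the effect is small if unblinding is rare or mostly follows surgery. The unclear scope for sponsor code breaks is a second fault, since sites could apply the rule differently. This is a should-fix point: the wording is certain, the size and direction of the loss are not, and the remedy is cheap.

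**What to change.** Replace the withdrawal sentence in Section 4.2.3 with text to this effect: unblinding does not end study follow-up. Unless the patient withdraws consent, the Week 16 MRI, surgical pathology and safety follow-up are still collected and analysed in the randomised arm, and unblinded patients are flagged. A regulatory code break by the sponsor that does not reach the site or the patient has no effect on participation.

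The current sentence may be the only text that bears on study drug after unblinding, because the mandatory stopping list in Section 4.6.2 does not mention it. The sponsor should therefore state the consequence for study treatment explicitly by reconciling Section 4.2.3 with Sections 4.6.1 and 4.6.2. No treatment rule is proposed here.

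The cost is a short wording change and a database flag, with no visits or procedures beyond the existing schedule.

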4.3 STUDY TREATMENT

4.3.1 Formulation, Packaging, and Handling

4.3.1.1 GDC-0032 and Placebo

GDC-0032 Drug Substance and Drug Product are manufactured according to current Good Manufacturing Practice guidelines for use in the clinical studies. Each lot of GDC-0032 for clinical studies is subjected to a series of quality control tests to confirm its identity, purity, potency, and quality.

GDC-0032 is provided for use in clinical studies as a white, film-coated, immediate-release tablet formulation of 2 mg strength.

Placebo tablets will be identical in shape and color to the 2-mg tablets of GDC-0032 and will be indistinguishable from the 2-mg tablets of GDC-0032. The ingredients in the placebo tablets are identical to those in the 2-mg tablets of GDC-0032, except for the absence of GDC-0032 active.

The GDC-0032 active and placebo tablets are packaged in high-density polyethylene bottles, are labeled for clinical use, and should not be stored above 25°C.

For further details, see the GDC-0032 Investigator's Brochure.

4.3.1.2 Letrozole

Letrozole will be labeled according to regulatory requirements in each country, as well as in accordance with International Conference on Harmonisation (ICH) Good Clinical Practice (GCP) and will be labeled for investigational use only. The Sponsor will provide letrozole free of charge to all study sites.

Refer to the letrozole (e.g., Femara[®]) Package Insert or summary of product characteristics (SmPC) for details on the formulation and storage of letrozole.

4.3.2 Dosage, Administration, and Compliance

4.3.2.1 GDC-0032 and Placebo

Patients will receive an oral, daily dose of 4 mg (two 2-mg tablets) GDC-0032 or placebo on a schedule of 5 days on/2 days off for a maximum of 16 weeks. Patients will take GDC-0032 or placebo at the same time of day \pm 2 hours, unless otherwise instructed. Patients will be instructed as to the number of tablets to take. Patients will be asked to record the time and date that they take each dose in a medication diary.

If a patient misses a GDC-0032 or placebo dose or vomits up a tablet, she should be instructed to skip that dose and to resume dosing with the next scheduled dose. Missed doses will not be made up. Patients will be instructed to bring their medication diary to each study visit for assessment of compliance. Patients will also be instructed to bring all unused tablets to each study visit for GDC-0032 or placebo accountability.

Guidelines for dosage modification and treatment interruption or discontinuation are provided in Section 5.1.

Any overdose or incorrect administration of study drug should be noted on the Study Drug Administration eCRF. Adverse events associated with an overdose or incorrect administration of study drug should be recorded on the Adverse Event eCRF.

4.3.2.2 Letrozole

Patients will receive an oral, daily dose of 2.5 mg letrozole for 16 weeks (or until time of surgery at the investigator's discretion). No dose modifications of letrozole are permitted. Any overdose or incorrect administration of letrozole should be noted on the letrozole

Administration eCRF. Adverse events associated with an overdose or incorrect administration of letrozole should be recorded on the Adverse Event eCRF.

Both GDC-0032 or placebo and letrozole should be taken together (in no particular order) at the same time each day \pm 2 hours, unless otherwise instructed.

